Description of parent measures: Data collection appointments will be scheduled with each parent-child dyad, on annual and semi-annual basis, as detailed in Form M. All parent/caregiver participants will complete baseline and annual assessments of parent- and child-level constructs, including: a brief sociodemographic background questionnaire also addressing prior healthcare use, child behavior therapy use, and HA/CI adherence (10 minutes); the 100-item CBCL Ages 1.5-5 or the 113-item CBCL Ages 6-18 (15

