
Certain protocols will be in place to address the potential risks associated with provision of services by parent coaches, rather than by mental health specialists. As a precaution, a letter signed by [name] or [name] will be sent to families with either (1) a child scoring at the 90th percentile or above on the CBCL internalizing or externalizing subscales at any assessment time point, or (2) a parent/caregiver indicating a "moderate" or higher level of depression according to scoring guidelines of the BDI-II at any assessment time-point. The letter will provide a referral to a local community mental health center for evaluation (as these families may be experiencing an immediate need for mental health services rather than only our brief preventive intervention). Families requesting more intensive services will be referred to the local community mental health center. Need for referral will be determined via parent coaches' feedback with the clinical supervisor during ongoing supervision, as well as by [name] and [name] review of child- and parent-level outcomes as they are assessed.

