
Regarding mental health "red flags", research staff members and parent coaches will be trained to recognize common signs and symptoms of child and adult mental health issues which may require additional intervention. Research staff will be trained to contact [name] if they observe red flags in child or parent participants. Parent coaches will be trained to contact their clinical supervisor if they observe red flags. [name] and the clinical supervisor will collaborate with [name] to determine the best course of action in each unique case. In these cases, we maintain a list of county-specific mental health and substance abuse treatment organizations for study staff to share with participants.

Regarding suicidality (i.e., statements of suicidal ideation and/or any response >0 on the suicidal ideation item on the BDI-II), research staff and parent coaches will be trained in a question-persuade-refer model with actions dependent on level of risk (see Additional Information attachments for "CHAMPS-DHH Safety Protocols" for Child Abuse/Neglect and Suicidality). REDCap will be programmed to automatically email an alert to [name], [name] and other research staff if the BDI questionnaire indicates suicidal thoughts or wishes. In all cases of encountering suicidal ideation, research staff and parent coaches will contact [name] and [name] as soon as possible after completing the listed steps. The situation will be documented and if confidentiality was broken, the adverse event will be reported as outlined under "Reporting Adverse Events," below.

In our previous studies with parents and children, we have very rarely encountered situations necessitating mandatory reporting or seeking assistance for suicidality. Parents who enroll in the study are aware and willing to have data collectors and interventionists meet with them and their children, so the study sample may be of lower risk than the general population. However, this training and support will be provided to all research staff and parent coaches so that all are prepared for these scenarios, no matter how unlikely they may be.

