### Data and Safety Monitoring

The IRB requires review and approval of data and safety monitoring plans for greater than minimal risk research or NIH-funded/FDA-regulated clinical investigations.

- If you are conducting greater than minimal risk research, or your clinical investigation is NIH-funded, describe your Data and Safety Monitoring Plan (DSMP). [Click here for additional guidance on developing a Data and Safety Monitoring Plan.](#)
- If this is a non-sponsored investigator-initiated protocol considered greater than minimal risk research, and if you are planning on using a Data and Safety Monitoring Board (DSMB) as part of your DSMP, [click here for additional guidance](#) for information to include with your IRB application.

We have two Data and Safety Monitoring plans: a DSMP for Aims 2, 3, and 5, and a DSMB for Aim 4, which is categorized as a clinical trial by NIH. Both are described below.

In addition to complying with NIH guidelines, our DSMP complies with the UK Institutional Review Board (IRB) and UK Office of Research Integrity (ORI) SOPs (<http://www.research.uky.edu/ori/>) for implementation of data and safety monitoring ([http://www.research.uky.edu/ori/human/SOPs\\_&\\_Policies.htm](http://www.research.uky.edu/ori/human/SOPs_&_Policies.htm)).

Risk assessment: Minimal risk:

All aspects of the proposed research involve minimal risk. We will be collecting data via key informant interviews, questionnaires, and focus groups. All study personnel (i.e., investigators, study coordinator, research assistants, data collectors, parent coaches) will be trained in the protection of human subjects, and all data collection and management procedures have been designed to minimize the risk of a confidentiality breach.

Description of potential adverse events:

Possible serious adverse events (SAEs) include: disclosures of abuse, neglect, domestic violence, or suicidal ideation. Unanticipated problems that are not SAEs include but are not limited to breach of confidentiality of study data, distress about answering questions about child behavior, and unanticipated negative reactions concurrent with or following study procedures. Protocol violations and instances of non-compliance include any deviations from the study protocol and/or the human subjects protection plan as approved by the IRB.

Description of safety monitoring for Aims 2, 3, and 5:

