The potential risks associated with provision of a behavioral intervention will be minimized with specific safety monitoring and precautions. Families with children scoring at the 90th percentile or above on the CBCL/1.5-5 at any assessment time point (i.e., at baseline or post-test) will be referred to the community mental health center for evaluation (as these children may require more intensive services). Similarly, any participants who endorse or report suicidal ideation or self-harm will be referred to the local emergency room for evaluation. Families requesting more intensive services also will be referred. Need for referral will be determined via parent coach report during clinical supervision, as well as by the PI's review of child- and parent-level outcomes as they are assessed.

All adverse events (AE) will be immediately reported to the PI, [name], who will be responsible for (1) reporting AE to the UK IRB, DSMB, and NIDCD, (2) assisting the DSMB with evaluation of all AE and determining whether the AE affects the risk/benefit ratio of the project, and (3) assisting the DSMB with determination of whether changes need to be made to the protocol and informed consent documents. All staff, including RAs, interviewers and interventionists, will be trained to recognize an AE and to undertake the proper reporting protocols in the event of an AE. Additionally, study Co-Investigators and the UK site PI, [name], will participate in the monitoring of the safety of the participants. These study personnel will meet as a team every six months and produce a written report that summarizes all items to be monitored, as follows:

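### The Aim 4 rules on suicidal ideation conflict: one section refers everyone to the emergency room, another makes the action depend on level of risk

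*Combined protocol and SAP*

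**What the plan says.** On suicidal ideation, the Aim 4 Description of safety monitoring gives an ungraded rule: "any participants who endorse or report suicidal ideation or self-harm will be referred to the local emergency room for evaluation". An earlier paragraph under the same heading speaks of emergency room referral for suicidality only as a possibility, to be explained during consent.

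The Records, Privacy, and Confidentiality section defines suicidality as statements of ideation and/or "any response >0 on the suicidal ideation item on the BDI-II", and says that "research staff and parent coaches will be trained in a question-persuade-refer model with actions dependent on level of risk". It points to attached safety protocols for the steps.

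On child behaviour, the Aim 4 safety section refers "Families with children scoring at the 90th percentile or above on the CBCL/1.5-5 at any assessment time point". The Records section sends a referral letter for "a child scoring at the 90th percentile or above on the CBCL internalizing or externalizing subscales at any assessment time point", and also when a parent reaches at least moderate depression on the BDI-II. The Aim 4 procedures use "the 100-item CBCL Ages 1.5-5 or the 113-item CBCL Ages 6-18".

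On event class, the opening of Data and Safety Monitoring, which leads into the plan for Aims 2, 3 and 5, states: "Possible serious adverse events (SAEs) include: disclosures of abuse, neglect, domestic violence, or suicidal ideation". The Aim 4 list places suicidal ideation among problems that are not SAEs, and emergency room visits among possible SAEs.

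**The concern.** Two parts of one approved plan give different instructions for the same answer on the same questionnaire. One is automatic and the other graded. Whoever handles a positive BDI-II ideation item, or a spoken disclosure, would act differently depending on which section is applied. The Aim 4 section also counts any departure from the approved human subjects protection plan as a protocol violation or non-compliance, so following the graded rule could itself be a recordable deviation from the automatic one.

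Participant safety comes first, but the safety data are also at stake. If the rule chosen determines whether an emergency room visit follows, it also influences whether an SAE is counted.

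**Working it through.** The plan states no figure to reproduce, so the check is a comparison of the texts.

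**Suicidal ideation.**

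| Place | Who is covered | Action |
|---|---|---|
| Aim 4, Description of safety monitoring (referral rule) | Anyone endorsing or reporting ideation or self-harm | Emergency room, no grading |
| Records, Privacy, and Confidentiality | Anyone stating ideation, or above 0 on the BDI-II item | Depends on level of risk |
| Aim 4, Description of safety monitoring (confidentiality paragraph) | Suicidality | Emergency room referral as a possibility |

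1. *Same group?* Yes. Answering the BDI-II item above 0 is endorsing ideation, and a statement of ideation is reporting it.
2. *Can both be obeyed?* Only if every risk level in the graded protocol includes emergency room referral. If any level does not, a participant at that level is referred under one rule and not under the other.
3. *Does the third text settle it?* No. It leans towards a conditional reading, but it could mean only that referral happens if ideation occurs.

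**Consequence for reporting.** Take one Aim 4 parent with the same answer under each rule.

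- Automatic rule: referral and, if the parent attends, an emergency room visit, which is a possible SAE. Under Reporting of adverse events, an SAE that is not fatal or life-threatening goes to the NIDCD within 7 days, with a detailed report within 15 days.
- Graded rule, at a level without emergency room referral: ideation only, listed as a non-SAE problem, to which the 7-day and 15-day limits do not apply.

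**Number of occasions.** The BDI-II is listed for baseline and annual assessments, so at most 4 occasions (0, 12, 24 and 36 months) and 125 × 4 = 500 parent questionnaires. Those enrolled after 3/2/2023 are expected to stop at 18 months, which gives 2 occasions; if that applied to all, 125 × 2 = 250. Mid-year visits use a subset of measures that the text does not itemise. The documents give no endorsement rate and say that, in earlier studies, the team very rarely had to seek help for suicidality.

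**CBCL.** The Aim 4 section names one form and no scale. The Records section names two scales and no form. Children enter at 3 to 6 years and are followed for up to 3 years, so they can reach 3 + 3 = 6 to 6 + 3 = 9 years, and the Ages 6-18 form will be in use. Read alone, the Aim 4 trigger omits that form; the Records trigger includes it. Both lead to community mental health, and acting on either trigger satisfies both.

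**BDI-II depression.** The Records section has the trigger and the Aim 4 section does not list it. The Aim 4 section does base need for referral partly on the PI's review of parent-level outcomes, so nothing in it forbids the trigger. This is an omission.

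**Event class.** The two lists belong to two separate monitoring plans. They overlap only for FCU-DHH parents interviewed in Aim 5: 20 according to Study Population, 10 according to the Aims 2, 3 and 5 safety monitoring text. That is 20/72 = 28% or 10/72 = 14% of intervention parents. No BDI-II is described for that interview, so the issue would arise there only from something said.

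**The case against.** The strongest reply is that the graded steps are in safety protocols attached to the application and handed to data collectors and coaches. Staff would work from those sheets rather than compare sections of the application. The sheets are not in the documents, so it cannot be shown that any risk level omits the emergency room. This stands as a limit on what can be said about actual practice. It does not remove the ungraded sentence from the approved plan, so the sheets and that sentence still have to agree.

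There are also real safeguards. A REDCap alert goes out when the BDI-II indicates suicidal thoughts, and staff must contact the study leads in all cases. A positive answer should therefore not go unnoticed; what is unsettled is the required action and how it is counted.

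Other sentences mention community mental health, or ideation with a plan and means. They describe confidentiality risks and what consent will stress. They are not referral rules, and the point does not rest on them.

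Timing limits the practical gain. By the 2024 continuing review two dyads remained to be recruited, study funding was to end in May 2025, and the current modification concerns Aim 5 stakeholder interviews. The documents do not say that Aim 4 assessments are finished, but few may remain. Final safety reporting still needs consistent classes.

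**Conclusion.** The contradiction on suicidal ideation holds and should be corrected. It assumes that at least one risk level in the unseen protocols does not lead to the emergency room. The effect on SAE counts further assumes that a referred parent attends and that the visit is classed as an SAE, which the plan lists only as possible. The number of cases is unknown and probably small. The primary PARYC analysis is not affected.

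The CBCL and BDI-II differences are lesser matters of wording and omission. The difference in event class matters only for Aim 4 parents interviewed in Aim 5.

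Three stronger readings are tempting, and the documents do not support them:

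- A reader might infer that all the referral rules are incompatible and staff cannot follow them together. That fits suicidal ideation only; acting on either CBCL or BDI-II depression trigger breaches nothing.
- A reader might infer that referral is a co-intervention applied differently by arm. The score-based triggers are not limited by arm, and both arms complete the assessments that feed them. Coach reports are a further route that only intervention families have, but this does not show that score-based referral differs.
- A reader might take the background figure of up to 50% with significant disruptive behaviour as the rate at which the CBCL trigger will be met. It is a general figure for DHH children, not a rate at or above the 90th percentile in this sample.

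**What to change.** 1. Reconcile the Records, Privacy, and Confidentiality text with both Aim 4 safety-monitoring paragraphs, so that one rule for suicidal ideation is stated once and cited elsewhere. The clinical leads decide its content; no rule is proposed here.
2. Make the CBCL wording (form, scale, threshold) and the BDI-II depression trigger agree between the Aim 4 safety section and the Records section, again as the clinical leads decide.
3. State one event class for suicidal ideation in Aim 4 parents who are interviewed in Aim 5.
4. Check the nationwide and Kentucky safety sheets against the result, and reissue them only if they differ.
5. Apply one event classification throughout final safety reporting, including to emergency room visits that follow a study referral.

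The cost is one IRB modification. No change to data collection or to the efficacy analyses is needed.

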#### Responsibilities of the DSMB

- Review and approve the research protocol(s) and plans for data and safety monitoring. The DSMB, in collaboration with the PI, will establish specific guidelines for safety monitoring. This will include a listing of events that should be reported immediately to the DSMB and the format of reporting cumulative data at intervals.
  - Review interim analyses of outcome data for safety and efficacy to determine whether the study should continue as originally designed, be changed, or be terminated. The DSMB will review clinical study performance information such as participant recruitment and retention, clinical center and resource center performance, and proposals for ancillary studies. It will advise the investigators and the NIDCD on these topics. The DSMB will also recommend whether and to whom outcome results should be released prior to the reporting of study results.
  - Review the primary study abstract(s) and manuscript(s) with regard to determining that the results are fairly presented and the conclusions appropriate.
  - Review published reports of related studies submitted to it by the NIDCD, the study leadership/investigators, or DSMB members to determine whether the monitored study needs to be changed or terminated.
  - Review proposed modifications to the study prior to their implementation (e.g., increasing target sample size, dropping an arm based on other study outcomes, modifying outcomes, etc.).
  - As soon as possible but within 10 business days following each DSMB meeting, provide the study leadership and the NIDCD with DRAFT written recommendations along with justification related to continuing, changing, or terminating the study.
  - As soon as possible but within 10 business days following each DSMB meeting, provide the study leadership and the NIDCD with a statement, where appropriate, concerning the impact on the study of individually observed or cumulative adverse events.
- Confidential outcome data will not be made available to individuals outside of the DSMB. Any release of outcome data to individuals outside of the DSMB will be reviewed and approved by the DSMB, the NIDCD, and the study leadership. No communication, either written or oral, of the deliberations or recommendations of the DSMB will be made outside of the DSMB except as provided for in these guidelines. Outcome results will be strictly confidential and will not be divulged to any non-member of the DSMB. Each member of the DSMB, including non-voting members, will sign a statement of confidentiality.

#### DSMB Membership

We will utilize the standing independent Data Safety Monitoring Board (DSMB) as chartered by the University of Kentucky Center for Clinical and Translational Science (CCTS) to monitor the safety of this study. Individuals on the DSMB will disclose any potential conflicts of interest, whether real or perceived, to the NIDCD program director on an annual basis. The NIDCD and the study leadership will make collaborative decisions regarding service by individuals with potential conflicts of interest or the appearance of conflicts of interest.

#### Meetings

The DSMB will meet semiannually or as needed, and will review subject recruitment, AE's, side effects, withdrawals, protocol violations, and inclusion/exclusion criteria. More frequent meetings will take place if necessary. Procedures and reports will follow NIDCD requirements for DSMB.

#### Reporting of adverse events

Our reporting plan follows NIDCD guidelines, which are based on 1996 and 2000 International Conferences on Harmonization, sections E2 and E6 Good Clinical Practice, and Health and Human Services (HHS) and FDA regulations. The UK Medical IRB has ultimate authority in assessing, managing, and reporting adverse events. Reporting of AEs to the PI will be completed by study staff using a standardized form recording the date of the event, type of event, whether the event was resolved, and resolution date.

The PI will report by telephone, fax, or email all deaths and life-threatening SAEs within 24 hours to the NIDCD program officer and to the UK IRB as specified in the protocol. This immediate report will be followed within 7 days by a detailed written report from the study coordinator or principal investigator to the NIDCD, IRB, and all participating investigators. All other SAEs will be reported to the NIDCD within 7 days, followed by a detailed written report to the NIDCD, IRB, and all participating investigators within 15 days. This report will include: (1) the appropriate identifying information for the research protocol; (2) a detailed description of the event; (3) an explanation of the basis for determining that the event represents an unanticipated problem; and (4) a description of any protocol changes or corrective action proposed or taken in response. In the case of SAEs found to be related to the research procedures, the PI will follow University of Kentucky procedures on critical incident review. The study protocol also will include necessary steps regarding staff and participant debriefing in the case of an SAE related to research procedures.

For non-serious AEs that are anticipated, the study coordinator/principal investigator will submit a written periodic report to the NIDCD, IRB, and all participating investigators. Unanticipated, non-serious AEs will also be reported. The DSMB, in consultation with the study team, will determine the attribution category. The IRB will determine whether any modifications to the study protocol or consent forms are required.

#### Adverse event attribution categories:

1. Unrelated: The AE is clearly not related to the intervention
2. Unlikely: The AE is doubtfully related to the intervention
3. Possible: The AE may be related to the intervention
4. Probable: The AE is likely related to the intervention

5. Definite: The AE is clearly related to the intervention

If required, the study coordinator will revise the study protocol and consent forms as appropriate for approval by the IRB, and notice of IRB approval will sent to the NIDCD program officer and the DSMB.

#### Reporting of other study-safety events

As the study is being conducted, the PI will also inform NIDCD promptly of any changes in recruitment or in the protocol that are relevant to safety, as well as any actions taken by the IRB as a result of its continuing (annual or more frequent) review of the study. In the event of any major changes in the status of an ongoing protocol, the PI will inform the NIDCD immediately. Such changes would include:

- Amendments to the protocol
- Temporary suspension of participant accrual, or of the protocol
- Any change in informed consent or IRB approval status
- Termination of participant accrual, or of the protocol
- Other problems or issues that could affect the human subjects in the study

